Last 10 Subjects. These subjects will take part in a double-blind, controlled, randomized, cross-over study over 3 sessions following their screening visit. At session 1 subjects will undergo electrical dose titration with the tDCS electrode configuration resulting from the 3 rounds of optimization using the same procedure as in the first 30 subjects to determine the lowest well-tolerated dose that suppresses the pupil dilation response to the Anxiety Task or Auditory Oddball Test, except that a maximum of 5 tDCS dosages will be tested at this session. At the second and third sessions (1 week apart) subjects will receive doseoptimized tDCS and the control treatment with order randomized along with 7.5% CO₂ (to evoke an LC response) for 20 minutes. The 7.5% CO₂ will be delivered pre-mixed as provided by Airgas. 7.5% CO₂ is commonly and safely used in the field of study. A mixture of CO₂ 7.5%/O₂ 21%/N 71.5% will be purchased premixed from Airgas and shipped to UCSF. At these sessions, the VAS-A and STA-I will be administered 5 minutes prior to and just after the 20 minute session and VAS-A will also be obtained at 5, 10, 15, and 20 minute points of the CO₂ inhalation. tDCS will be administered during the last 5 minutes of the 20 minute CO₂ inhalation period. Subjects will be monitored for an hour post-session for safety and will undergo study physician assessment to determine suitability to leave. Following the 2nd treatment session participation will end except that subjects will be called the next day to assess for adverse effects and appropriate care will be given if any are found.

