R33 Phase: 60 subjects will participate in a double-blind, randomized, controlled, parallel-group trial. They will be randomized to either active or control treatment and at the first post-screening visit they will undergo electrical dose titration as described above for the treatment they are randomized to. For all titrations, during the 5 minutes between tDCS treatments an unblinded member of the study team not having contact with the subjects will compute their Anxiety Task or Auditory Oddball Test response (these tests will be used to determine optimal dosing in terms of the tDCS level that blocks the pupil response in these tests) and convey to the tDCS treatment physician whether to continue or stop titration. Subjects randomized to the control treatment will undergo a sham titration where the stop level will be randomly selected from the distribution of titration outcomes occurring in the R21 phase. Subjects will then return in 1 week and undergo optimal dose tDCS or control treatment for a single treatment session as described in the prior paragraph. Primary outcome will be the VAS-A "fearful" rating obtained at the end of tDCS/CO₂ inhalation. Anxiety Task or AOT pupil responses will be obtained every 10 minutes after the end of the tDCS/CO₂ inhalation period to map the duration of persistent effects on LC (heart rate and skin conductivity will also be obtained as exploratory measures). At the end of this session participation will end except that subjects will be called the next day to assess for adverse effects and care given if necessary. Data from the R21 phase will be used to provide justification for the larger R33 study, and prior to initiation of the R33 phase, the study will be submitted to the IRB for review/approval.

8.5 BACKGROUND AND SIGNIFICANCE: Briefly provide the background and significance of this study (e.g.

why is this study needed) (space limit: one half page):

If this is a first in humans study, please summarize the safety data from the animal studies. For pediatric drug or device studies, please identify if this is the first study in pediatric populations.

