2. **Transcranial Direct Current Stimulation (tDCS):** tDCS involves non-invasive transcranial electrical stimulation using direct current with a sustained intensity of a few milliamperes and duration of up to tens of minutes. Administered in this way tDCS is a safe procedure (See Bickson et al., 2016 attached). Evidence from relevant animal models indicates that brain injury by such Direct Current Stimulation occurs at predicted brain current densities (6.3–13 A/m) that are over an order of magnitude above those produced by tDCS such as we will administer it (Bickson et al., 2016). To date, the use of conventional tDCS protocols in human trials (40 min, 4 milliamperes, 7.2 Coulombs) has not produced any reports of a Serious Adverse Effect or irreversible injury across over 33, 200 sessions and 1000 subjects with repeated sessions and including a wide variety of subjects, including persons from potentially vulnerable populations (Bickson et al., 2016). tDCS will be administered with a multichannel direct current stimulation device (NeuroConn DC stimulator MC-4, neuroCare). This device can be programmed so that the operator doesn't know the combination of electrodes being used for stimulation, and, thereby allow double-blinding. The active tDCS electrode configuration to be used will be determined with the 3 round iterative procedure described above; based on electric field modeling and personalized electrical dose titration to find the lowest dose that is well-tolerated and engages the

target in terms of inhibiting the Anxiety Task or AOT pupillary response and pain-induced conditioned fear response. Electrical dosage will be personalized for each subject by titrating dosage (gradually increasing) until the dosage is found that is both well-tolerated (no more than mild discomfort on a 5-point Likert scale) and suppresses the pain-induced conditioned fear response. If the 5-point Likert tolerability rating is greater than "mild discomfort" or if maximum amperage is reached without effect on the conditioned fear response then subject participation will terminate.

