current state with respect to those feelings from 1 (not at all) to 4 (very much so). It will be administered just before and just after CO₂ administration.

5. **Generalized Anxiety Disorder-7 (GAD-7)**. The 7 item questionnaire may be administered at screening visits to identify anxiety state and trait correlations with pupil physiology.
6. **Beck Anxiety Inventory (BAI)**. This questionnaire may be administered at screening visits to identify anxiety state and trait correlations with pupil physiology.
7. **Adverse Effects (AE) Assessment**. The Systematic Assessment for Treatment Emergent Events (SAFTEE) will be used to monitor AEs. It is reliable and valid and used by [name] in prior studies.

Attach any unpublished instruments in the 'Other Study Documents' section of the Initial Review Submission Packet form after completing the study application. Published instruments should NOT be attached.

8.12 * BIOSPECIMEN COLLECTION: Are you drawing any blood or collecting other biosamples (e.g. tissue, buccal swabs, urine, saliva, hair, etc.): (REQUIRED)

Yes No

8.25 STATISTICAL METHODS: Briefly summarize the methods and types of analyses that will be performed:

All dependent measures will be tested for distribution normality and meeting homogeneity of variance requirements for parametric statistics. Data transformations will be conducted where indicated.

1. Primary Hypotheses.

R21. Testing R21 hypotheses equates to testing if the "Go-No-Go" criteria for proceeding to the R33 are met.

1) Hypothesis 2a: We can identify an electrode configuration for active tDCS that is well-tolerated (5-point Likert scale rating mild discomfort) and significantly suppress the Anxiety Task or Auditory Oddball

Task (AOT) pupil dilation response in 8/10 subjects in the 3rd round of treatment optimization. The Anxiety Task or AOT response will be determined using a repeated measures analysis of variance * (RMANOVA) with condition (common vs rare) as the independent measure and pupil diameter as the dependent repeated measure. If there is a statistically significant difference between the two conditions during treatment it will be assumed that suppression did not occur.

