- None of the above

10.7 INCLUSION CRITERIA: Briefly describe the population(s) that will be involved in this study. Include anyone that data will be collected from or about (e.g. patients, healthy controls, caregivers, providers, administrators, students, parents, family members, etc.):

Inclusion/Exclusion criteria were chosen to allow us to meet study aims and are comparable to those used in [name] prior study of transcranial alternating current (tACS) vestibular stimulation of healthy controls. Inclusion Criteria. 1) Age between 21-65; 2) Use of effective method of birth control for women of childbearing capacity; 3) Willing and able to provide informed consent; 4) Have a significant difference between the mean pupil diameter in response to rare vs common tones in the Auditory Oddball Test (AOT) or the Anxiety Task; 5) The 10 subjects in the R21 cross-over study and all of the R33 subjects must have a 26% increase in VAS-A "fearful" response to 7.5% CO₂ at the first CO₂ challenge session; 6) Able to follow study procedures.

10.8 EXCLUSION CRITERIA: List any exclusion criteria (e.g. reasons why someone would not be included in the study):

Exclusion Criteria. 1) Current or past Axis I DSM-IV disorder based on the MINI; 2) Current or past history of substance abuse or dependence (excluding nicotine) based on history or positive urine toxicology; 3) Current unstable medical condition; 4) Any current neurological condition or medical condition that is known to affect pupillary function, mood/anxiety, or neurologic function generally; 5) Pregnancy based on Urine Pregnancy Test; 6) Women who are breast feeding; 7) Use of medications known to affect CNS function within 5 half-lives screening; 8) Use of magnet controlled or programmed devices such as pacemakers, programmable ventriculoperitoneal shunts, or vagal nerve stimulators.

10.9 * RESEARCH CONDUCTED ON PATIENT CARE WARDS: Do any study activities take place on patient care units at UCSF medical facilities: (REQUIRED)

Yes No

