11.0 Recruitment and Consent

11.1 * RECRUITMENT METHODS: What kinds of methods will be used to identify potential participants for recruitment (check all that apply): (REQUIRED)

- Medical records review
- Recruitment registry
- Re-contact of participants from the investigators' previous studies
- Referrals from colleagues (attach the 'Dear Colleague' letter or other recruitment materials you will provide to colleagues)
- Referrals from the community / word of mouth
- Advertisements (flyers, brochures, radio or t.v. ads, posting on clinical research sites or social media, presentation of the study at community events/media, etc.)
- Online recruiting tool such as TrialSpark
- CTSI Recruitment Services unit
- Other method (describe below)

Attach your recruitment materials (e.g., flyers, ads, recruitment letter templates, email text, etc.) in the Other Study Documents section of the Initial Review Submission Packet Form.

11.3 DETERMINATION OF ELIGIBILITY: How, when, and by whom will eligibility for recruitment be determined:

Flyers are placed around the UCSF campus and on the clinicaltrials.gov providing basic study information and eligibility criteria. Potential subjects will contact the study coordinator who will conduct a brief phone screen to determine initial eligibility criteria prior to scheduling the in-person screening visit. If the subject meets pre-screening criteria, an in-person screening visit will be scheduled at which time the subject will undergo screening procedures in [name] laboratory conducted by a study clinician. Normal healthy control subjects will be recruited and, following signing of informed consent, screened in the laboratory for whether they meet inclusion/exclusion criteria by [name] or other study clinician and a study coordinator trained by and working under the supervision of [name]. Assessments carried out during this visit will include a medical, psychiatric, and medication history, physical examination, urine drug screen, pregnancy test, and MINI. Those meeting entry criteria will then undergo the Anxiety Task or Auditory Oddball Task (AOT) administered by [name] or the study coordinator. Those with a statistically significantly greater pupil diameter response to the Anxiety Task or the cues for the rare vs common stimuli in the AOT will continue in the study and be scheduled for return visits.

Flyers will be placed around the UCSF campus and in non-investigator faculty offices.

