The study structure is such that there will be 4 cohorts of subjects each consisting of 10 subjects. Each of the first 3 cohorts will be stimulated with a different tDCS electrode configuration to determine if we can find one which is tolerable and inhibits locus coeruleus activity (as indicated by inhibition of a pupil dilatory response). After each cohort we will carry out an interim analysis to determine if this was the case (80% had tolerability ratings of 2 or less and there was statistically significant inhibition of the pupillary response to the anxiety task or auditory oddball task). Each of these interim analyses will be reported to the DSMB. If after the 3 cohorts are completed and if none of the 3 tDCS configurations tested meet the success criteria, then the study will cease. If one of the tDCS configurations meets the success criteria then an additional 10 subjects will be run using the successful tDCS configuration and using 7.5% CO2 instead of the anxiety task or auditory oddball test to elicit a pupillary response.

13.3 * DATA AND SAFETY MONITORING BOARD (DSMB): Will a Data and Safety Monitoring Board (DSMB) be established: (REQUIRED)

Yes

No

13.4 DSMB DETAILS: Provide details from the DSMB's charter, including meeting frequency, and affiliations and qualifications of members: If the DSMB has not yet been established, submit these details to us as they become available.

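### Eligibility, titration and the Go count each accept either pupil task, and nothing requires that one subject be assessed on the same task throughout

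*Combined protocol and SAP*

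**What the plan says.** Four steps depend on a pupil task, and each is worded as an alternative.

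- **Eligibility.** Section 10.7, item 4, asks for a "significant difference between the mean pupil diameter in response to rare vs common tones in the Auditory Oddball Test (AOT) or the Anxiety Task". Section 11.3 keeps in the study "Those with a statistically significantly greater pupil diameter response to the Anxiety Task or the cues for the rare vs common stimuli in the AOT".
- **Titration.** In 8.4, the last ten R21 subjects are titrated to the "lowest well-tolerated dose that suppresses the pupil dilation response to the Anxiety Task or Auditory Oddball Test". For all titrations, the R33 paragraph has an unblinded team member compute the "Anxiety Task or Auditory Oddball Test response".
- **Go count.** Hypothesis 2a in 8.25 needs 8/10 third-round subjects with a tolerable configuration that suppresses the response on either task. The operational rule is "If there is a statistically significant difference between the two conditions during treatment it will be assumed that suppression did not occur".
- **Interim criterion.** Section 13.2 asks for inhibition that reaches significance in the "response to the anxiety task or auditory oddball task".

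Two further places name a different target. Aim 3 in 8.3 ties the R33 dose to the oddball task alone. Section 8.9, item 2, titrates until the dose "suppresses the pain-induced conditioned fear response", although 8.9, item 1, lists that test separately from the other two tasks.

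**The concern.** The rule in 8.25 treats absence of a significant difference as success. That inference needs evidence that the subject shows a difference on that task when tDCS is off. The screening criterion is the natural source of this evidence, but it serves only if the later assessment uses the same task. As written, a subject may qualify on one task and be titrated and counted on the other. If the subject does not respond to the second task, the test is non-significant with probability 0.95 at one dose (level 0.05), whatever tDCS does.

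The Go count could then include subjects in whom nothing was suppressed. Their titrated dose is carried to the CO₂ sessions, and the R21 titration outcomes supply the distribution from which R33 sham-titration stop levels are drawn (8.4). If both tasks were run and success on either counted, each dose would also offer two chances.

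**Working it through.** **The plan's own figures.** The 8/10 in 8.25 agrees with the 80% in 13.2. No error rate or power is stated for it, so there is no operating characteristic to reproduce. The 25% pupil non-response rate enters only the enrolment figures. For R21, 30/0.75 + 10/(0.75 × 0.5) = 66.7, or 67 against 68 stated. For R33, 60/(0.75 × 0.5) = 160 against 172 stated, which leaves about 7% (1 − 160/172) for other screening failures.

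**Inputs.**
- Go threshold: 8 of 10 (8.25).
- Up to five doses (8.4).
- Non-response: 25%, given for the oddball test in 10.1 and for the fear conditioning paradigm in 8.4. None is given for the Anxiety Task, so using it there is an assumption.
- Assumed: within-subject level 0.05; power w of 80% or 90% to detect a true responder's effect in one run; independence between doses, tasks and subjects; tolerability met; titration stops at the first non-significant result.

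**What the 25% means.** Sections 10.7 and 11.3 define response as a significant result. The 25% is therefore read as the share of non-significant screening results, which includes true responders who were missed. The share q of true non-responders solves 0.95q + (1 − w)(1 − q) = 0.25.
- w = 0.80: q = 0.05/0.75 = 0.067.
- w = 0.90: q = 0.15/0.85 = 0.176.
- w = 0.60: q = −0.15/0.55 = −0.27, which is impossible.

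**Per-subject success with inert tDCS over k doses.**
- Same task, response shown: p = 1 − w^k.
- Every subject on the other task: p = q(1 − 0.05^k) + (1 − q)(1 − w^k).

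The chance of passing is P(X ≥ 8) for X ~ Bin(10, p).

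| Power | Doses | Same task: p | P(≥8/10) | All mismatched: p | P(≥8/10) |
|---|---|---|---|---|---|
| 80% | 1 | 0.200 | 0.00008 | 0.250 | 0.0004 |
| 80% | 5 | 0.672 | 0.31 | 0.694 | 0.37 |
| 90% | 5 | 0.410 | 0.014 | 0.514 | 0.065 |

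**If both tasks were run at every dose and either counted**, a subject who responds to both would have p = 1 − (w²)^5.
- 80% power: 1 − 0.64^5 = 0.893, so P(≥8/10) = 0.92.
- 90% power: 1 − 0.81^5 = 0.651, so P(≥8/10) = 0.26.

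If a share q does not respond to the second task, these become 0.93 and 0.42.

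**With an on- versus off-tDCS test instead.** With inert tDCS, a significant change at level 0.05 at any of five doses has probability 1 − 0.95^5 = 0.226. This gives P(≥8/10) = 0.0002, even if changes in either direction are counted.

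**The case against.** The case on the other side is substantial.

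- **No section describes a switch of task.** One task per subject may well be intended. This stands as to intent, and the all-mismatched column is an upper case. But 10.7 admits subjects on either task while Aim 3 names only the oddball task and 8.9 the conditioned fear response, so a mismatch is written into the text.
- **Running both tasks looks impractical.** In 8.9, item 3, a visit has 4 to 6 Anxiety Task trials of 12 minutes with 5-minute breaks: 4 × 12 + 3 × 5 = 63 minutes to 6 × 12 + 5 × 5 = 97 minutes. Section 11.13 allots 1.5 hours to each later visit. The either-task figures are therefore conditional on something that the plan does not describe.
- **Baseline trials exist.** In 8.9, item 3, half the trials for subjects 1–30 run without tDCS or with sham. A non-responder would be visible there. But no significant baseline is required, and the rule in 8.25 does not use these trials.
- **The interim wording in 13.2 asks for significant inhibition.** That presupposes a response and would largely close the gap. It is not reconciled with 8.25.
- **The count alone does not give a Go.** Section 8.25 lists other R21 criteria, including suppression of the CO₂ pupil response in a randomised cross-over, which does not rely on non-significance. This stands and limits the consequence.
- **The root cause is reading non-significance as suppression.** This also stands: 0.31 arises at 80% power over five doses with the same task throughout.

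A reader might also treat the 25% as the share of true non-responders. That gives 1.0% at one dose and 80% power. At 60% power it gives 8.6%, and counting either of two tasks at 60% power gives 24%. The documents do not support these figures. The 25% already contains missed responders, so adding misses again counts them twice, and 60% power cannot coexist with a 25% screening failure rate.

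**Conclusion.** The point holds as a gap in the rules. Eligibility, titration, the Go count and the interim criterion are not tied to one task per subject, and the titration target differs between 8.3, 8.4 and 8.9. Given the rule in 8.25, screening no longer guarantees that a suppressed subject had a response to suppress.

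The effect of the mismatch alone is small at one dose. Over five doses, with every subject mismatched, it adds about 0.06 to the chance of a false pass at 80% power (0.31 to 0.37) and about 0.05 at 90% (0.014 to 0.065). It would be much larger only if both tasks were run and either counted. These figures depend on the assumed power, on independence, and on applying the 25% to whichever task is used.

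It does not follow that subjects will be switched between tasks, or that the Go decision as a whole is likely to be false. The documents show neither.

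**What to change.** 1. In 8.3, 8.4, 8.9, 8.25, 10.7 and 13.2, reconcile the passages so that the task with the significant screening response is recorded for each subject. Use that task for the pupil assessment at titration and for the Go count, and give no credit for suppression on any other task. If both tasks are significant at screening, name one before titration. Sections 8.3 and 8.9 must be brought into line with 8.4. This point takes no position on the dose rule itself.
2. Reconcile 8.25 with 13.2 by defining suppression as a significant reduction from the off-tDCS to the on-tDCS response on the recorded task. The off-tDCS or sham trials in 8.9, item 3, supply the comparison for Anxiety Task subjects in the first 30. The plan should name the equivalent runs for the oddball test and for later subjects.

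Step 1 alone would leave the 0.31 untouched; step 2 deals with it.

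The cost is mainly wording. Step 1 needs no extra testing, but the team loses freedom to switch tasks. Under step 2, a subject with real but modest suppression may fail to reach significance, so 8/10 becomes harder to meet. The power of the on/off comparison should be considered before it is adopted.

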This application responds to RFA-MH-15-300 (Exploratory Clinical Trials of Novel Interventions for Mental Disorders [R21/R33]) by proposing to translate neuroscience findings into a novel non-pharmacologic treatment for Acute Fear, a Research Domain Criteria (RDoC) construct common to many DSM defined anxiety disorders. The neuroscience findings which serve as the basis for this effort are an extensive preclinical body of work documenting that the region of the brainstem known as the locus coeruleus (LC) plays a key role in mediating symptoms of Acute Fear. We capitalize on evidence that LC activity can be non-invasively measured with pupillometry and our pilot data indicating that we can modulate LC activity with transcranial direct current stimulation (tDCS) applied via electrodes attached to the skin/scalp. Our approach is to develop tDCS as a means of inhibiting LC activity and then determine if this diminishes symptoms of Acute Fear.

Our translational effort will consist of two stages, a 2 year R21 phase where we establish feasibility, tolerability, safety, and proof-of-concept (POC) in terms of capacity to engage the neural target, followed by a 3 year R33 parallel-group, double blind, controlled trial. In the R21 phase we will employ an iterative approach where we use electric field modeling with a realistic head model to identify promising treatment electrode placements which we will test across a series of electrical doses in 3 cohorts of healthy controls to attempt to identify a tDCS treatment electrode configuration with which

we can identify a dosage in each subject that is: (1) tolerable (5-point Likert ratings of no more than mild discomfort); and (2) engages the target neural circuitry by transiently inhibiting LC activity as reflected in prevention of the pupil dilation response in the anxiety task or to rare stimuli in the auditory oddball task (AOT), tasks which reliably activate LC. If successful we will proceed to a 3 year R33 parallel group trial where 60 healthy volunteers are randomized to electrical dose-personalized active tDCS vs an active control therapy (tDCS that delivers the same skin current density as the active but does not affect LC) here clinical symptoms Acute Fear, the primary outcome, are elicited by inhalation of 7.5% CO₂. Future development viability will be assumed if there is preliminary evidence that engaging the target (inhibiting LC) safely diminishes clinical Acute Fear symptoms.

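### Section 8.9 sets each subject's dose, and ends participation for lack of effect, on a conditioned fear response that the plan never describes, while the rest of the plan uses the Anxiety Task or AOT

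*Combined protocol and SAP*

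**What the plan says.** Section 8.9, item 2, uses the conditioned fear response in three sentences.

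- **Engagement:** the dose sought is one that engages the "target in terms of inhibiting the Anxiety Task or AOT pupillary response and pain-induced conditioned fear response".
- **Titration:** "Electrical dosage will be personalized for each subject by titrating dosage" upward until it is well tolerated and "suppresses the pain-induced conditioned fear response".
- **Termination:** besides poor tolerability, "if maximum amperage is reached without effect on the conditioned fear response then subject participation will terminate".

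Item 1 of 8.9 (Pupillometry) also lists a pain-induced conditioned fear test among the occasions for recording pupil size, separately from the Anxiety Task or AOT.

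Elsewhere the target is different. The study summary ahead of item 4.2 defines engagement as "prevention of the pupil dilation response in the anxiety task or to rare stimuli in the auditory oddball task". In 8.4, the last 10 R21 subjects are titrated to "determine the lowest well-tolerated dose that suppresses the pupil dilation response to the Anxiety Task or Auditory Oddball Test", "using the same procedure as in the first 30 subjects". For R33, and for all titrations, 8.4 has an unblinded team member compute the Anxiety Task or AOT response and tell the treating physician whether to continue, and it adds that "these tests will be used to determine optimal dosing in terms of the tDCS level that blocks the pupil response in these tests".

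**The concern.** Dose-personalised tDCS is the intervention under test, so the response used to set the dose is part of its definition. The plan gives two answers to that question.

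For dosing, the procedure in 8.4 can be followed. For a subject who reaches maximum dose without suppression, 8.4 gives no instruction. The only one in the plan is the termination sentence in 8.9, item 2, and it refers to a response with no stated procedure. If staff set the sentence aside as stale, no rule remains for that subject. If they follow it, a subject whose Anxiety Task or AOT response is suppressed, and who therefore counts towards success under 8.25 and 13.2, could be removed because conditioned fear was unaffected.

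**Working it through.** No power or sample-size figure carries this point. The check sets the passages side by side, with two short calculations.

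**1. Where the conditioned fear test or response appears.** It is named once in 8.9 item 1 and three times in item 2, so 1 + 3 = 4 mentions. The 11 items of 8.9 are pupillometry, tDCS, Anxiety Task, VAS-A, GAD-7, BAI, AOT, CO₂, skin conductance, ECG and field modelling. None gives a procedure for it: 0 of 11.

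**2. What the other sections use.**

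| Section | Role | Test |
|---|---|---|
| Study summary | Engagement | Anxiety Task or AOT |
| 8.3, Aim 3 | R33 dose | AOT only |
| 8.4, first 30 R21 subjects | Rising doses | Anxiety Task or AOT |
| 8.4, last 10 R21 subjects | Dose | Anxiety Task or AOT |
| 8.4, R33 | Dose | Anxiety Task or AOT |
| 8.5 | Proof of concept | Anxiety Task or AOT |
| 8.9, item 3 | Rising doses | Anxiety Task |
| 8.25, Hypothesis 2a | Go/no-go | Anxiety Task or AOT |
| 13.2, interim analysis | Success of a configuration | Anxiety Task or AOT |
| 8.9, item 2, titration and termination | Dose and removal | Conditioned fear only |

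**3. Is there another subject-level rule for lack of effect?** The withdrawal rules in 13.2 cover tolerability (a rating of 3 or more), safety and the subject's own request. The interim rule in 13.2 stops the study if no configuration succeeds and says nothing about an individual. Section 8.4 gives a continue-or-stop procedure but no outcome for a subject unsuppressed at maximum dose. So item 2 is the only such rule.

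**4. Is it a stale label?** Sections 8.4 and 10.1 carry the same enrolment paragraph. The first ties a 25% screening failure to a fear conditioning paradigm, the second to the AOT. The enrolment arithmetic shows whether one test or two are counted, using 25% failure for the task and 50% for CO₂:

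- One task screen, R21: 30/0.75 + 10/(0.75 × 0.50) = 40 + 26.7 = 66.7, against 68 stated.
- One task screen, R33: 60/(0.75 × 0.50) = 160, against 172 stated. The difference of 12 is a 93% pass rate (160/172) on the other, unquantified criteria.
- Two separate task screens at 25% each, R21: 30/0.5625 + 10/(0.5625 × 0.50) = 53.3 + 35.6 = 88.9, well above 68.
- Two separate task screens, R33: 60/(0.5625 × 0.50) = 213.3, well above 172.

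The stated totals fit a single screening task under two names. That supports the stale-label explanation but does not prove it.

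**5. Reach as worded.** Item 2 covers every subject, and 8.4 gives the last 10 R21 subjects the same titration as the first 30: 30 + 10 = 40 in R21. It also covers the active share of the 60 in R33.

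**6. What simple rewording would do in R33.** Section 8.4 randomises before titration. Controls receive a sham titration whose stop level is drawn at random from R21 outcomes, so they cannot fail for lack of suppression. A lack-of-effect termination would therefore act on the active arm alone, after randomisation. As an illustration, assume 1:1 allocation (30 active; the ratio is not stated) and 70% to 90% titration success (assumed; in the pilot 4 of 5 subjects showed suppression with some configuration). The active subjects left are 30 × 0.70 = 21 to 30 × 0.90 = 27, against 30 controls.

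**The case against.** The strongest reply is that this is a terminology slip. A response that nobody measures cannot trigger a termination, and every working description of titration uses the Anxiety Task or AOT. The Anxiety Task pairs a tone with finger stimulation on half its presentations, which is the structure of fear conditioning, so the disputed phrase may be its old name. Most of this stands. Against it, item 1 lists the conditioned fear test separately, item 2 joins the two with *and*, and item 3 says the buzz is not meant to cause pain. Even if the two are the same task, the titration and termination sentences would leave out a subject titrated on the AOT.

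Four stronger readings are tempting and not supported.

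- **Subjects will be misdosed or wrongly removed.** The documents show a contradiction on paper, not a likely event.
- **An undisclosed painful procedure is being run.** Section 12.2 has no entry for one, but it has none for the AOT either, and it asks only for risks not listed in 12.1, which includes a line on pain or discomfort.
- **Item 2 flatly contradicts its own engagement sentence.** The conflict is partial: that sentence requires both components, and the titration sentence drops one.
- **The eligibility rules in 10.7 and 11.3 contradict item 2.** They use the Anxiety Task or AOT, but they concern entry to the study and not dosing.

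**Conclusion.** The point holds as an inconsistency in an operative rule, and it should be fixed. Section 8.9, item 2, bases titration and the plan's only subject-level lack-of-effect termination on a response that is named four times and described nowhere. The dosing and success rules elsewhere rest on the Anxiety Task or AOT pupil response. For dosing, 8.4 supplies a fallback; for termination there is none.

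The number of subjects affected, and any difference in dose, cannot be computed, because the documents give no agreement between the tests. The wording reaches all 40 R21 subjects and the R33 active arm. That is its scope, not a count of people harmed. That the phrase is a leftover is an inference from the text, which the investigator needs to confirm. The range of 21 to 27 active subjects rests on assumed allocation and titration success, and shows only why the corrected rule should not be carried into R33 unchanged.

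**What to change.** First ask the investigator whether any conditioned fear test is run apart from the Anxiety Task and AOT. The same answer settles which test the 25% belongs to in 8.4 and 10.1. If no separate test is run:

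1. In the engagement, titration and termination sentences of 8.9, item 2, replace the conditioned fear wording with *the pupil dilation response to the Anxiety Task or AOT*, and delete the conditioned fear test from item 1.
2. Align Aim 3 in 8.3, which names the AOT alone.
3. Limit the lack-of-effect termination to R21 titration. State in 8.4 that R33 active subjects without suppression are treated at their highest tolerated dose and analysed as randomised. Leave the tolerability rules as they are.

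If a separate test is run, describe it in 8.9 and bring 8.4, 8.25 and 13.2 into line with it.

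Steps 1 and 2 are wording only. Step 3 is a small design decision. Nothing adds data, visits or procedures. The price of step 3 is some dilution in R33: if unsuppressed subjects gain nothing, the expected mean difference is multiplied by the titration success rate, so by 0.70 to 0.90 over the range assumed above. Titrating each subject on the task that qualified them at screening is an optional preference and not part of the error.

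Make the change before further titration, and at the latest in the IRB submission that 8.4 requires before R33.
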